#### Enrollment:

Eligible patients will be randomized to metformin IR or fluvoxamine or fluvoxamine + metformin or ivermectin or ivermectin + metformin or placebo and will receive the study drug by courier or mail service with every effort made to deliver the drug same-day or via overnight delivery.

#### Medication regimen:

*Metformin or Placebo:* Participants will be advised to take 1 pill by mouth on Day 1, ideally in the evening; and 1 pill by mouth approximately every 12 hours starting Day 2; and 1 pill by mouth in the AM and 2 in the PM day 6 and onwards, and to take pill at the end of a balanced meal and to stay upright for at least an hour after taking it.

*Fluvoxamine or Placebo:* Participants will be advised to take 1 pill by mouth on Day 1, ideally in the evening, and 1 pill by mouth approximately every 12 hours for Days 2 - 14.

Ivermectin: Participants will be advised to take any blister-packed tablets on an empty stomach.

The following data points may also be collected, if available, by self-report or EHR review:

- Name; Date of birth; Medical record number (if applicable); Phone number; Email
- o Contact information for family members to assist with follow-up if needed
- Age; biologic sex; Race; Ethnicity; Insurance status (if available); Zip code
- o Location of initial sample collection for diagnosis, Location of assessment
- Date and time of initial sample collection for diagnosis
- Date and time of positive test result for COVID-19
- Date of first symptoms
- Date of first fever, if applicable (temperature  $>100.5^{\circ}$ F)
- Patient-reported comorbidities [for example: hypertension (requiring or not requiring medication), diabetes mellitus (insulin or non-insulin dependent), coronary artery disease, myocardial infarction, congestive heart failure (with preserved or reduced ejection fraction, if known), pacemaker or AICD, asthma (with or without emergency department evaluation and / or hospital admission in the past year), chronic obstructive pulmonary disease, chronic bronchitis, chronic steroid use, history of transplant (with type), arrhythmias including atrial fibrillation, dialysis, angina, pulmonary hypertension and obstructive sleep apnea, renal disease, liver disease, tobacco and alcohol use history, recent or current pregnancy or breastfeeding history, and height and weight at study start and completion.]
- Self-reported home medications [for example: antihypertensives, insulin, non-insulin diabetes medications, corticosteroids (inhaled, systemic), other immunosuppressants hydroxychloroquine, other COVID-directed treatments or vaccines] or home oxygen use

- Use of outpatient COVID-directed treatments (such as Tylenol, ibuprofen, azithromycin, or others); whether or not they received the 2020/21influenza or COVID-19 vaccines.
- Medication adherence, known exposures, symptoms and side effects

The following data points may also be collected, if available, by self-report or EHR review:

- Vital signs at presentation to ER or urgent care (if recorded)
- Clinical laboratory results at presentation (if recorded)
- Hospital admission (with date, if applicable)
- Date of death (if applicable)
- Study withdrawal, with date and time (if applicable)
- 5.4.2 Retention:

All study staff members will be informed of the importance of retention and steps to prevent missing data. RC's will be advised to contact participants a second time per patient contact point if they are not able to reach the participant after the 1st contact. RC's may call, video, text, or email with patients on Day 2 to assess side effects or questions. If patients experience side effects, the RC's may remind patients of approaches to minimize side effects (See Section 4.3), and to advise the patients that side effects usually subside after about 5 days.

#### 5.4.3 Lab Collection:

Labs will be considered optional if patients want to participate but not collect the nasal swab and/or stool. For interested and willing patients, labs will be done on approximately Day 1, 5, and 10.

The SARS-CoV-2 PCR may be assessed via self-collect anterior nasal swab, which may be done over phone or video with the RC if the patient prefers this aid. Detailed instructions for the patient are in Appendix B, the patient manual.\*

The GFR blood tests may be collected by the clinic, mobile phlebotomy, or finger-prick, with the option of it being done while on secure video or phone with the RC if the patient prefers this aid. Blood will be collected in a microtainer tube and placed in approved shipping materials that will then be returned to the lab via courier or mail.

Stool sample collection is optional and would be done with a self-collect microbiome kit. Patients will be given detailed lab collection procedures for each test.

Missing biospecimens will not constitute protocol deviations.

5.4.4 Seeking Medical Care:

Patients will be advised to seek medical care, as they would if they were not in the study, including other treatments of Covid-19. Participants will be advised that the distribution of home oxygen monitors is not meant to prevent them from seeking medical care, and that they should seek medical care as they would whether they were in the study or not.

5.5 Follow-up Procedures:

CONFIDENTIAL

Data on clinical progression may be collected on any consented patient by EHR review, from contact if patient not available, by patient self-report (phone, survey, email, text), or by vital records search.

RC's may contact patients on Day 2 to assess side effects or questions. If patients experience side effects that they find distressing, the RC's will discuss approaches to minimize side effects (See Section 4.6 Dose Modification), and to advise the patients that side effects usually subside after about 5 days.

Participants will be asked to track symptoms (including temperature and oxygen saturation), and medication adherence daily. Patients will receive a thermometer and oxygen saturation monitor with their study drug (details below). Study personnel will attempt to contact with patients about every 2 to 3 days during the 14-day intervention window to review study drug adherence, and review symptoms for possible adverse events.

Patients will be followed for 28 days for disease severity. Follow-up contact with patient or family and electronic medical record review will determine the primary and secondary efficacy endpoints.

A patient who has a visit to an emergency department for COVID-19 related symptoms, (determined by current CDC definition of COVID-19 related symptoms or treating team), or hypoxia (two measurements of O2 saturation  $\leq 93\%$  or supplemental oxygen required to maintain saturation  $\geq 93\%$ ) will have achieved a positive result for the primary outcome.

Patients who experience a primary outcome before enrollment (i.e. ED visit at which they received their +SARS-CoV-2 result) will be followed for occurrence of a primary or secondary outcome after T0 (Day 1 in the study).

- Patients who are hospitalized will stop the study drugs.
- Secondary outcomes will be assessed at 14 and 28 days, including in patients who drop out of doing the study tasks. EHR search of outcomes will be assessed of all patients who enroll.
- Patients in the treatment arm who visit an urgent care or emergency department and are sent home without being admitted should continue the study drug through day 14, unless otherwise directed by the treating physician in the emergency department or urgent care.
- Long-Covid symptoms will be assessed at approximately 1-month intervals after the completion of the 14-day study treatment period.

#### Oxygen Saturation:

For the daily oxygen saturation recording, participants will be asked to measure their oxygen level ideally in the afternoon or evening. They may take a reading at any time, especially if they feel short of breath or are breathing faster than normal. If they have an oxygen saturation  $\leq 93\%$  on room air on 2 readings or more, they will be advised to call their doctor's office (or go to the ED if they feel they need to). If a study participant develops a decrease in oxygen saturation to less than 90% on room air on >2 readings,

the research staff will direct them to seek emergency medical care at the nearest ED. Research staff may call 911 on behalf of the patient, or otherwise engage the patient's medical provider, if they feel the patient is not able to do this on their own.

Referral to medical care: If the research staff feels a patient is unwell, they will advise the patient to reach out to their doctor. Physician investigators may also evaluate the participant via phone/telehealth and direct them for further care if needed.

When a participant is directed to seek emergency medical care, they will be instructed to identify themselves to EMS or to the ED staff as having been diagnosed with COVID-19.

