## 3.2 Laboratory Endpoints:

The first approximately 62 patients who are enrolled will be analyzed as a sub-study of continuous lab outcomes comparing those on metformin versus placebo: C-reactive protein (CRP) level; albumin level; viral load; as well as microbiome changes (stool sample is optional for participants), from baseline to days 5 and 10. (See Section 13 for more information)

\*Patients will be asked to take a second reading if they have a reading  $\leq 93\%$  and to hold a handwarmer for 5 minutes first to obtain good blood flow; to take the reading while sitting up; and advised to place the oximeter on the 4th finger (where skin is thinner).

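### Emergency referral for saturation below 90% needs at least three readings, while the milder 93% rule and the hypoxia endpoint need only two

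*Protocol*

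**What the plan says.** The Oxygen Saturation part of section 5.5 sets two escalation rules, one after the other.

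- **Saturation of 93% or lower.** The rule applies "on room air on 2 readings or more, they will be advised to call their doctor's office". Going to the emergency department is left to the participant's own judgement.
- **Saturation below 90%.** When it falls "to less than 90% on room air on >2 readings", "the research staff will direct them to seek emergency medical care at the nearest ED". Staff may also call 911 or involve the participant's medical provider.

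Three other provisions bear on how many readings will exist and when staff will see them.

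- Section 5.5 counts a participant as having reached the primary outcome through "hypoxia (two measurements of O2 saturation" at or below 93%.
- The oximeter footnote under section 3.2 says: "Patients will be asked to take a second reading if they have a reading" of 93% or lower. It adds steps to improve the signal (warming the hand, sitting up, choice of finger).
- Routine recording is once a day. Extra readings are permitted: "They may take a reading at any time, especially if they feel short of breath". On staff contact, section 5.5 says: "Study personnel will attempt to contact with patients about every 2 to 3 days during the 14-day intervention window".

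**The concern.** The lower and more dangerous value requires more confirmation than the milder one, and no reason is given. The text at hand also never asks the participant for the additional reading.

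What is at stake is the safety instruction itself. This is a remote trial in which home oximetry is one of the main warning signals. Staff who hold two readings below 90% are not required by the protocol to send the participant to emergency care, although the same protocol accepts two readings as established hypoxia at a higher saturation.

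**Working it through.** No sample size, power or error-rate figure is involved, and the protocol states no figure to reproduce. The check compares the rules as conditions on *n*, the number of low readings.

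| Provision | Threshold | Condition on *n* |
|---|---|---|
| Section 5.5, advice to call the doctor | 93% or lower | *n* ≥ 2 |
| Section 5.5, hypoxia for the primary outcome | 93% or lower | *n* = 2 suffices |
| Section 3.2 footnote, readings requested | 93% or lower | 1 + 1 repeat = 2 |
| Section 5.5, staff direct to emergency department | below 90% | *n* > 2, i.e. *n* ≥ 3 |

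Take a participant whose first reading and requested repeat are both below 90%, so *n* = 2.

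1. Advice rule: 2 ≥ 2, met. The participant is advised to call the doctor and may choose the emergency department.
2. Hypoxia criterion: two measurements, met.
3. Emergency rule: 2 > 2 is false, not met.

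The shortfall is 3 − 2 = 1 reading, and the requested procedure does not generate it.

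The time from the second reading below 90% until the emergency rule is met depends on when a third such reading is taken and reported. The rule gives no time window, so I assume that a reading on a later day counts.

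- Participant chooses to repeat at once: minutes.
- Third value is the next daily recording: about 24 hours.
- Staff learn of the two readings at a contact, and nobody reports until the next one: about 2 to 3 days, or 2 × 24 = 48 to 3 × 24 = 72 hours.

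With the rule changed to *n* ≥ 2, step 3 becomes 2 ≥ 2 and is met as soon as the requested repeat is known to staff.

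The protocol does not say how many participants would have exactly two readings below 90%, so no count is estimated.

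**The case against.** The strongest objection is that everything rests on one comparison sign, and the protocol is not careful with such signs. Supplemental oxygen is tied to saturation above 93% in section 3.1 but to 93% or above in section 5.5. The top ivermectin weight band is above 124 kg in section 4.1 but 124 kg or above in section 4.2. Two or more readings may well have been meant, and a sign lost when the PDF was read cannot be excluded. This makes a slip plausible, but it does not remove the point. The same paragraph keeps its less-than-or-equal sign and puts the other rule's count in words, and the text at hand says more than two. If the source document says two or more, the sponsor can confirm that at once and nothing needs changing.

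A second objection is that three readings could be deliberate. Directing someone to emergency care is a stronger action than advising a call, and home oximeters give false lows. That would be a defensible choice, but the protocol does not state it. The section 3.2 footnote already builds its precautions against false lows into the second reading. A three-reading rule would also need a request for the third.

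Third, other safeguards exist. Staff who think a participant is unwell advise contact with the doctor, and physician investigators may assess remotely and direct further care. Sections 5.4.4 and 5.5.2 tell participants to seek care as they would outside the study. Nothing stops staff from acting after two readings or asking for a third on the call. All of this stands and narrows the gap. But these routes are discretionary, lead only to the doctor, or depend on the participant, and none is a required direction to emergency care tied to a saturation value.

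Finally, the 48 to 72 hour figure needs several things to go wrong together, so it is an upper scenario and not an expected delay. The wait before staff first hear of low readings comes from the contact schedule and would remain after the fix. Appendix B, with the patient manual, is not shown and might request a third reading.

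**Conclusion.** The concern holds as the text stands. The below-90% rule needs one more reading than the milder rule, than the hypoxia criterion and than the repeat procedure supplies. What is missing at two readings is the mandatory staff direction to emergency care; advice to call the doctor is still triggered.

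No effect on the primary endpoint, power or between-arm comparison is claimed, because two readings below 90% already satisfy the hypoxia criterion whether or not the participant is sent for care. The conclusion assumes that the sign is as printed and that the patient manual does not ask for a third reading. Confidence is medium for those two reasons. It should be corrected because it sets a safety threshold and the correction is small.

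**What to change.** In section 5.5, Oxygen Saturation, make the below-90% rule act on two or more readings, worded like the 93% rule. If the clinical team does want three, keep the count but require a third reading immediately after two below 90%. In either case, check that the patient manual gives the same instruction.

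The cost is one line of protocol text and the manual check. The downside is possibly a few more emergency referrals prompted by false low readings.

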#### 5.5.1 Survey Data Collection:

Participants will be given a hard-copy symptom log to capture COVID-19 related symptoms daily (Appendix B). Patients will be asked to record their medication adherence, their temperature, and their oxygen saturation with a home O2 monitor every day for the 14 days of participation.

The symptom log may also be available by Part-11 approved means (such as via text or app). For patients not using app, RC's will assess whether the symptom logs are being filed out daily at each contact point with patients. Adherence with taking the medication will be assessed via self-report daily in the log or software to record adherence.

Survey questions will be listed in a physical paper study log that is included in the study box that is sent to patients. Patients can fill out the survey on these paper logs and then send a picture of the logs to study staff (no identifying information on the pages of the logs); patients can also receive the survey questions via Part 11-certified electronic means; or patients can report the survey question answers to the RC over the phone if they prefer.

## 5.5.2 Timeline of Events:

Every attempt will be made for the contact points with patients to be done in the way that they prefer (i.e. text, phone, email, video):

**Day 1 Contact:** Verify receipt of study drug, participant starts study drug. If multiple participants live in the same household, they will be reminded to keep all of their study materials labeled with their own participant ID and separated from the other participants.

- Phone or video visit to walk through procedures for obtaining lab values if the patient desires.
- RC will arrange for the lab samples to be returned.
- Patient records symptoms (via symptom log adapted from FDA suggestions, Appendix B), RC does not need to collect over phone.

## **Day 2 Contact:**

- Patient records side-effects (PROMIS diarrhea survey, Appendix C)
- Patient records symptom/adherence log (adapted from FDA suggestions, Appendix B)
- Assessment of clinical progression

• Query for medication-related side effects / AEs

**Day 3/4:** RC will follow-up results of GFR for patients for whom GFR was indicated. If the GFR is < 45ml/min, the RC will have the patient return the remaining study drug in one of the return envelopes provided and will arrange for this shipping.

Day 3, 4: Symptom/adherence log (adapted from FDA suggestions, Appendix B)

#### **Day 5 Contact:**

- Symptom/adherence log (adapted from FDA suggestions, Appendix B)
- Assist with return shipping of optional labs (viral load, stool)
- Assess clinical progression

**Day 6-9:** Symptom/adherence log (adapted from FDA suggestions, Appendix B)

#### Day 10 Contact:

- Symptom/adherence log (adapted from FDA suggestions, Appendix B)
- Assess clinical progression (Query for hospitalization or ER visit or SAEs)
- Assist with return shipping of optional labs (viral load stool)

Day 11-13: Symptom/adherence log (adapted from FDA suggestions, Appendix B)

#### Day 14 Contact:

- Symptom/adherence log (Appendix B)
- Assess clinical progression

## Day 28 Contact:

- Symptom log (adapted from FDA suggestions, Appendix B)
- Assess clinical progression (Query for hospitalization or ER visit or SAEs that occurred between Day 14 and Day 28)
- Assess other medicines used during study period

A vital status search will be conducted on all randomized patients.

Days are +/- 3 days, for the first 14 days every attempt will be made to capture data +/- 1 day.

Patients will be advised to seek medical care for symptoms in the same way that they would if they were not in the study.

Participants will be reimbursed for their time via a trackable means (i.e. Clin card or Visa card), after completion of these study activities: enrollment; Day 1 labs; Day 5 labs; Day 10 labs; Day 14 log returned; and Day 28 follow-up.

Monthly Contact: Patients will be assessed approximately once/month for 9 months after the completion of their Day 28 contact to assess for ongoing symptoms suggestive of post-acute sequelae of COVID-19. Patients will receive reimbursement for each of these monthly follow-ups completed.

5.6 Study Duration:

14 days of treatment with follow-up, and a follow-up survey at 28 days then monthly for 9 months.

## Schedule of Assessments:

Symptoms: Days 1- 14, 28. Side effects: Day 2 AE's/SAE's: Days 2, 5, 10, 14, 28 Clinical Progression: Days 5, 10, 14, 28 PASC: Monthly after Day 28

5.7 Retention:

We will make every effort to keep participants engaged through the entirety of the study so as to minimize missing data (for example regular calls, texts, emails, assessment via vital records search, and contact with family members if needed). The principal investigators have recent experience working with patients on COVID-19 trials, and they will leverage this experience.

## 6.0 Study Population

6.1 Study Population:

Adults age 30-85 years with no prior history of SARS-CoV-2 infection and with BMI in overweight or obesity category. We will not exclude patients who have diabetes, but we will exclude patients on insulin or a sulfonylurea. Symptoms are not a requirement to enroll in the because of their subjective nature and because of wanting to start patients on study drug early in the disease course.

6.2 Inclusion and Exclusion Criteria:

Inclusion criteria	Exclusion criteria
- Positive laboratory test for active SARS-CoV-2	- Hospitalized, for COVID-19 or other reasons.
viral infection based on local laboratory standard	- Symptom onset greater than 7 days before
(i.e. +PCR) within 3 days of randomization.	randomization (symptoms not required for inclusion).
- no known history of confirmed SARS-CoV-2	- immune compromised state (solid organ transplant,
infection	bone marrow transplant, AIDS, on chronic high dose
- Age $\geq$ 30 years and $<$ 85 years	steroids)
- BMI $\geq 25$ kg/m  by self-report height/weight or	- Hepatic impairment (Child-Pugh B and C) or
$>= 23 \text{kg/m}^2$ in patients who self-identify in	that in the opinion of the investigator, would affect safety
Asian or Latinx background. 	- Inability to obtain informed consent
- Has an address and electronic device for	- Enrollment in another blinded RCT for COVID-19
communication	- Already received an effective (FDA approved/EUA*)
- GFR>45ml/min within 2 weeks for patients	therapy for COVID-19 (currently monoclonal antibody
>75 years old, or with history of heart, kidney, or	treatment)
liver failure.	- Alcohol use disorder

- Other unstable medical condition or combination of home medications that in the view of the PI make it unsafe for the individual to participate

 
History of severe kidney disease i.e.:
 
Stage 4 or 5 CKD, or Estimated Glomerular Filtration Rate (eGFR) of < 45ml/min/1.73 m^2
 
Other kidney disease that in the opinion of the investigator would affect clearance
 
Unstable heart failure (Stage 3 or 4 heart failure)
 
Current use of metformin, fluvoxamine, or ivermectin
 
Bipolar disease: individuals who report they have bipolar disorder or are taking medication for bipolar disorder (lithium, valproate, high-dose antipsychotic), unless the investigator concludes that the risk for mania is unlikely (i.e. it is doubtful that the patient actually has bipolar disorder).
 
allergic reaction to metformin in the past
 
allergic reaction to ivermectin in the past
 
allergic reaction to ivermectin in the past
 
current loa loa or onchocerciasis infection
 
typhoid, BCG, or cholera vaccination within the 14- days or 3 days after
 

 
Medication Exclusions:
 
cimetidine, hydroxychloroquine, insulin, sulfonylurea, dolutegravir, patiromer, ranolazine, tafenoquine.
 
rasagiline, selegiline, or monoamine oxidase inhibitors, linezolid, methadone
 
Duloxetine, methylene blue
 
Tizanidine, ramelteon, sodium picosulfate
 
Alosetron, agomelatine, bromopride, dapoxetine, tamsimelteon, thioridazine, urokinase, pimozide
 

The following medications may not need to be excluded when dose for that individual is considered alongside the low dose of fluvoxamine being used and other medications being used. The PI or site PI may review and decide if the patient should be excluded from the fluvoxamine arms:
1. Taking SSRIs, SNRIs, or tricyclic antidepressants, unless these are at a low dose such that a study investigator concludes that a clinically significant interaction with fluvoxamine (ie either serotonin syndrome or TCA overdose) is unlikely (examples: participant takes escitalopram but only at 10mg daily; that dose plus 100mg fluvoxamine would be insufficient to cause serotonin syndrome; or, participant takes amitriptyline but only at 25mg

	nightly; even if fluvoxamine inhibits its metabolism, it would be an insufficient dose to cause QTc prolongation or problematic side effects). Risk Class C, monitor therapy .
2.	Individuals who take alprazolam or diazepam and are unwilling to cut the medication by 20% (rationale: fluvoxamine modestly inhibits the metabolism of these drugs). Risk Class C, monitor therapy
3.	Participants taking theophylline, clozapine, or olanzapine (drugs with a narrow therapeutic index that are primarily metabolized by CYP 1A2, which is inhibited by fluvoxamine) will be reviewed with a study investigator and excluded unless the investigator concludes that the risk to the participant is low (this would be unlikely; example: participant takes clozapine only as needed and is willing to avoid it for the 14 days of the study).
4.	Patients will be advised that there is a small risk that the following substances will be affected by fluvoxamine, but that significant effects are not likely at the low dose being used:
	1. caffeine, nicotine, melatonin. Risk Class C, monitor therapy
5.	Taking warfarin-also known as Coumadin, NSAIDs, and Aspirin (rationale: increased risk of bleeding), phenytoin (rationale: fluvoxamine inhibits its metabolism), clopidogrel (rationale: fluvoxamine inhibits its metabolism from pro-drug to active drug which raises risk of cardiovascular events), and St John's wort (rationale: fluvoxamine + St John's wort are considered contraindicated because of the risk of
	serotonin syndrome) Risk C, monitor therapy.

\*Additional COVID-19 treatments to exclude will be decided by a panel of at least 3 Co-Investigators on this study. The additional treatments to exclude will be documented and submitted to the IRB but may be implemented before formal IRB approval is complete. We take this approach because of the rapidly changing treatment landscape of COVID-19.

6.3 Vulnerable Populations:

By nature of the disease and the fact COVID-19 is a rapidly evolving pandemic, with uncertain clinical course but potentially significant morbidity and mortality, all participants enrolled in this study are considered to be vulnerable. Some participants have additional characteristics that add to this vulnerability. Our criteria for inclusion and exclusion of each of these groups is summarized below, followed by our rationale and additional safeguards built into our study design. Our group has significant experience enrolling vulnerable patients in emergency care trials, and experience with a diverse population of potential participants in high stress situations.

COVID-19 is disproportionately impacting low-income communities and persons of color, and these reasons are multifactorial. It is important to include individuals of diverse backgrounds in

CONFIDENTIAL

this research. It is also important to not present this research in a coercive way to individuals with low income and who come from traditionally marginalized backgrounds. We have chosen participating sites throughout the US based on sampling diverse populations throughout the US (i.e. areas serving primarily Black and Latinx populations), areas where there are high incident rates, and areas with experienced PI's.

